### **3. DESCRIPTION OF DESIGN AND TRIAL POPULATION**

#### **3.1 OVERALL TRIAL DESIGN AND PLAN**

The study will be performed open-label, in a multiple-dose, matched group design with moderate renal impaired and healthy male and female subjects. In this exploratory study it is considered reasonable to aim for at least 25% of either gender.

It is planned to include altogether 20 participants in the trial, of which up to 10 subjects with moderate renal impairment. All subjects will receive over 4 weeks 10 mg of BI 1467335 once daily, the maximum therapeutic target dose in the upcoming phase II studies in a NASH population. Each renally impaired subject will have a healthy subject matched for gender, race, smoking status, age (within  $\pm 10\%$ ) and BMI (within  $\pm 10\%$ ). They will build a pair for later evaluation.

Renal impaired subjects will receive a subject number starting with      while healthy subjects will receive a subject number starting with

The study will follow a staggered inclusion starting with a subcohort of 3 renally impaired subjects. For this initial subcohort there will be a safety review meeting between sponsor and investigator to decide whether the study can proceed as planned. Matched healthy subjects will be only included if the corresponding renally impaired subjects have completed the study.

Additional safety reviews may be conducted at any time if deemed necessary by the investigator or sponsor.

An overview of all relevant trial activities is provided in the [Flow Chart](#). For visit schedule and details of trial procedures at selected visits, refer to [Sections 6.1](#) and [6.2](#), respectively.

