### **3.3.5 Replacement of subjects**

In case some subjects do not complete the trial, the trial clinical monitor together with the trial pharmacokineticist and the trial statistician are to decide if and how many subjects will be replaced. A replacement subject will be assigned a unique study subject number.

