#### **4.1.4 Drug assignment and administration of doses for each subject**

This trial is an open-label study, with a matched-parallel group design. All subjects will receive the same treatment, 10 mg q.d. over 28 days. The inclusion of matched subjects of Group 2 will be done on an individual basis after corresponding renal impaired subjects of Group 1 have completed the treatment period.

If intake of study medication occurs at study site, the trial medication will be administered to the subjects, while in a sitting position, as an oral dose together with about 240 mL of water under supervision of the investigating physician or an authorised designee. The so-called four-eye principle (two-person rule) should be applied for administration of trial medication.

Proprietary confidential information © 2018 Boehringer Ingelheim International GmbH or one or more of its affiliated companies

In case of ambulatory intake subjects are required to contact the site by phone to confirm the intake of study medication.

In principal, for both hospitalized and ambulatory conditions intake of study medication should be performed following an overnight fast, which is to start no later than 10 h before the scheduled dosing. During ambulatory conditions subjects may have breakfast about 1 h after drug intake. If a subject misses his morning dose by 6 h, the subject should omit drug intake on this specific day.

To ensure a dosing interval close to 24 h, the administration or intake (during ambulatory periods) of trial medication should take place at a similar time every day.

Subjects will be kept under close medical surveillance from the evening of Day -1 to the morning of Day 2, from the evening of Day 13 to the morning of Day 15, and from the evening of Day 27 to the morning of Day 29. During the first 2 h after drug administration, subjects should not lie down (i.e. no declination of the upper body of more than 45 degrees from upright posture except for medical examination), or to sleep. For restrictions with regard to diet see [Section 4.2.2.2](#).

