## **7.3 PLANNED ANALYSES**

Adherence to the protocol (such as inclusion/exclusion criteria, times of measurement, compliance with intake of trial medication, treatment dispensing errors, prohibited concomitant medication, completeness and consistency of data) will be checked. Important protocol violations will be identified no later than in the Report Planning Meeting and provided in the Trial Statistical Analysis Plan (TSAP).

The following analysis sets will be defined for this trial:

Further analysis sets will be defined in the TSAP, if needed.

- Randomised set (RS):

This subject set includes all subjects who were randomized, i.e., who have been assigned a study subject number, whether treated or not.

- Treated set (TS):

This subject set includes all subjects in the RS who were documented to have received one dose of study drug. This is the full analysis set population in the sense of ICH-E9.

- PK analysis set (PKS):

Plasma and urine concentration data and parameters of a subject will be included in the statistical pharmacokinetic (PK) analyses if they are not flagged for exclusion due to a protocol violation relevant to the evaluation of PK (to be decided no later than in the Report Planning Meeting) or due to PK non-evaluability (as revealed during data analysis, based on the criteria specified below). Exclusion of a subject's data will be documented in the CTR.

Proprietary confidential information © 2018 Boehringer Ingelheim International GmbH or one or more of its affiliated companies

Relevant protocol violations may be

- Incorrect dose of trial medication taken
- Use of restricted medications.

Plasma and urine concentrations and/or parameters will be considered as non-evaluable, if for example

- the subject experienced emesis that occurred at or before two times median  $t_{max}$  of the respective treatment (Median  $t_{max}$  is to be determined excluding the subjects experiencing emesis),
- missing samples/concentration data at important phases of PK disposition curve.

The PK analysis set (PKS) includes all subjects in the TS who provide at least one PK parameter that was defined as primary or secondary endpoint and was not excluded according to the description above. Thus, a subject will be included in the PKS, even if he/she contributes only one PK parameter value to the statistical assessment.

- PK statistical analysis set (PKS-stat):

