This subject set includes all subjects from the PKS who built a subject pair of renal impaired subject and his matching healthy volunteer control and provide at least one PK parameter that was defined as primary or secondary endpoint and was not excluded according to the description above.

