### 6.3 SUBJECT SETS ANALYSED

- Treated set (TS):

This subject set includes all subjects who were dispensed study medication and were documented to have taken at least one dose of investigational treatment.

This is the full analysis set population in the sense of ICH-E9 ([1](#)). It is used for safety analyses.

Plasma and urine concentration data and parameters of a subject will be included in the statistical pharmacokinetic (PK) analyses if they are not flagged for exclusion due to a protocol deviation relevant to the evaluation of PK (to be decided no later than in the Report Planning Meeting) or due to PK non-evaluability (as revealed during data analysis, based on the criteria specified below). Exclusion of a subject's data will be documented in the CTR.

Relevant protocol deviations may be:

- Incorrect dose of trial medication taken
- Use of restricted medications.

Plasma and urine concentrations and/ or parameters of a subject will be considered as non-evaluatable, if for example:

- the subject experienced emesis that occurred at or before two times median  $t_{max}$  of the respective treatment (Median  $t_{max}$  is to be determined excluding the subjects experiencing emesis),
- missing samples/ concentration data at important phases of PK disposition curve.

  

- PK analysis set (PKS):  
The PK analysis set (PKS) includes all subjects in the TS who provide at least one PK parameter that was defined as primary or secondary endpoint and was not excluded according to the description above. Thus, a subject will be included in the PKS, even if he/she contributes only one PK parameter value to the statistical assessment.
- PK statistical analysis set (PKS-stat):  
This subject set includes all subjects from the PKS who built a subject pair of renal impaired subject and his matching healthy volunteer control and provide at least one PK parameter that was defined as primary or secondary endpoint and was not excluded according to the description above.

The descriptive analysis of PK concentrations will be based on the ADS ADPC as described at the beginning of [Section 7](#).

Table 6.3: 1 Analysis sets for endpoints/data description

Endpoint/data description	Analysis set		
	TS	PKS	PKS-stat
Safety assessments		X	
Primary and secondary analyses of primary, secondary and further PK endpoints			X
Further analyses of primary and secondary PK endpoints		X	
Descriptive evaluations of primary, secondary and further PK endpoints		X	

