### **Section 7.1.3 of the CTP:**

*The statistical model used for the analysis will be an ANOVA (analysis of variance) model on the logarithmic scale including the effect "degree of renal impairment" as a fixed effect as well as subject pair as a random effect. The model is described by the following equation:*

$$y_{ik} = \mu + \tau_k + s_i + \varepsilon_{ik} \text{ where}$$

$y_{ik}$       *logarithm of response (endpoint for relative bioavailability evaluation, measured on the degree of renal impairment  $k$  for subject pair  $i$ ),*

$\mu$  the overall mean,

$s_i$  the  $i$ th subject pair (each renal impaired subject has his own matching healthy control),  $i=1, \dots, 10$ ,

$\tau_k$  the  $k$ th degree of renal impairment,  $k = 1$  for normal and  $k=2$  for moderate renal impaired,

$\varepsilon_{ik}$  the random error associated with the  $k$ th degree of renal impairment for subject pair  $i$ .

Point estimates of the ratios of the geometric means (T/R) for the endpoints and their two-sided 90% confidence intervals (CIs) will be provided.

To this end, the PK endpoints will be log-transformed (natural logarithm) prior to fitting the ANOVA model. For each endpoint, the difference between the expected means for  $\log(T)$ - $\log(R)$  will be estimated by the difference in the corresponding adjusted means (Least Squares Means), and a two-sided 90% confidence interval based on the t-distribution will be computed. These quantities will then be back-transformed to the original scale to provide the point estimate and 90% CIs for each endpoint.

The analysis will be accomplished by using the XPKISTAT macro, based on PKS-stat (design BWU).

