### **7.5.2 Secondary endpoints**

The same analyses as for the primary endpoints will be performed for the secondary endpoints  $C_{\max,14}$  and  $AUC_{\tau,14}$  of BI 1467335 on Day 14 (refer to Section [7.4](#)).

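### Do impaired subjects who stop early, and so never get a matched control, need a further ratio analysis for Day 1 and Day 14?

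*Protocol*

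**What the plan says.** Controls enter one at a time, after their impaired partner. Protocol 3.1 states: "Matched healthy subjects will be only included if the corresponding renally impaired subjects have completed the study". Protocol 4.1.4 places the same step "after corresponding renal impaired subjects of Group 1 have completed the treatment period". Under either wording, an impaired subject who stops dosing early is not given a control.

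The ratios for Day 1, Day 14 and Day 28, with their 90% confidence intervals, come from a log-scale ANOVA with subject pair as a random effect (Protocol 7.1.3, SAP 7.4). For Day 14, SAP 7.5.2 says: "The same analyses as for the primary endpoints will be performed for the secondary endpoints". All are fitted to PKS-stat, defined in SAP 6.3 as "all subjects from the PKS who built a subject pair of renal impaired subject and his matching healthy volunteer control".

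The wider PKS is more lenient. Protocol 7.3 says that "a subject will be included in the PKS, even if he/she contributes only one PK parameter value to the statistical assessment". SAP Table 6.3:1 uses the PKS for the descriptive evaluations and for further analyses of the primary and secondary PK endpoints. On replacement, Protocol 3.3.5 says only that three named functions "are to decide if and how many subjects will be replaced".

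**The concern.** Day 1 Cmax and AUC0-24 are primary endpoints, and a subject who stops in week 2 has a complete Day 1 profile. Leaving that profile out of the ratio discards good data.

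The loss is also one-sided. A control who stops after Day 1 has already formed a pair and, as PKS-stat is worded, stays in unless a replacement control takes over. Only the impaired group is selected on completion. If the impaired subjects with the highest exposure were the ones who stopped, the Day 1 and Day 14 ratios would understate the effect of renal impairment, which is the quantity the trial is meant to estimate. Replacing the stopper restores the number of pairs but not the stopper's data. No visible part of the SAP gives a ratio with a confidence interval that keeps such subjects.

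**Working it through.** **Inputs.** From the documents: 10 pairs (Protocol 7.6); a two-sided 90% interval based on the t-distribution (Protocol 7.3.1); 9 active subjects at 10 mg in the earlier 28-day study (Protocol 2.3), all of whom completed (Protocol 1.2). The documents give no CV, within-pair correlation or stopping rate for impaired subjects. These are assumptions here: CV 60% or 100%; within-pair correlation r = 0.3; 10% or 20% stopping; odds ratio (OR) for stopping of 2 or 4 per SD of log exposure; correlation ρ of 0.2, 0.5 or 1 between Day 1 exposure and the exposure that drives stopping. The plan states no precision figure to reproduce.

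**Width of the planned interval.** The log SD is √ln(1+CV²), which is 0.5545 at CV 60% and 0.8326 at CV 100%. The interval factor is exp(t(0.95, 9 df) × log SD × √(2(1−r)/10)), with t = 1.833 and √(1.4/10) = 0.374.
- CV 60%: exp(1.833 × 0.5545 × 0.374) = 1.46.
- CV 100%: exp(1.833 × 0.8326 × 0.374) = 1.77.

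**Bias of the pairs-only ratio.** The factor is exp((1−r) × ρ × log SD × mean z of completers). Under logistic stopping, the mean z of completers is about −0.066 (10%, OR 2) and −0.216 (20%, OR 4).

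| Factor on the Day 1 ratio, CV 60% | ρ = 1 | ρ = 0.5 | ρ = 0.2 |
|---|---|---|---|
| 10% stopping, OR 2 | 0.97 | 0.99 | 0.995 |
| 20% stopping, OR 4 | 0.92 | 0.96 | 0.98 |

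At CV 100% the range is 0.96 to 0.88 with ρ = 1 and 0.99 to 0.975 with ρ = 0.2. If stopping is unrelated to exposure, the factor is 1.00. If low exposures stop more often (20%, OR 0.5, ρ = 1, CV 60%), it is 1.05.

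**Effect on coverage.** In simulation at CV 60% and ρ = 1, the 90% interval from pairs alone covers about 90% of the time at 10% stopping with OR 2, and about 87 to 88% at 20% with OR 4.

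**Shift without a stopping model.** For given r, adding m unpaired stoppers to 10 pairs changes the log ratio by (1−r) × m/(10+m) × (mean log exposure of stoppers − mean log exposure of paired impaired subjects). If stoppers have twice the completers' geometric mean:
- one stopper: 2^(0.7/11) = 1.045;
- two stoppers: 2^(1.4/12) = 1.084.

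At half the exposure the shifts are 0.957 and 0.922.

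**Deliberate worst case.** If the two highest of ten impaired exposures stop and are not replaced (CV 50%, r = 0.3, true ratio 1), pairs alone give 0.90, with an interval factor of 1.45 on the remaining 8 pairs. The random-pair model on the PKS gives 1.00.

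**How likely is a stopper?** The chance of at least one among ten is 1 − (1−p)^10: 40%, 65% and 89% at p = 5%, 10% and 20%. With 0 of 9 stopping at 10 mg, the one-sided 95% upper limit is 1 − 0.05^(1/9) = 28%, so the earlier study does not rule these rates out. If nobody stops, the two analyses are identical.

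**Cost of the alternative.** Unpaired subjects bring contrasts that are not matched on gender, race, smoking status, age and BMI. If those factors differ 1.25-fold in effect, the wider analysis shifts by 1.25^(0.7/11) = 1.014 for one stopper or 1.25^(1.4/12) = 1.026 for two. That is smaller than the shift from a stopper with doubled exposure, but larger than the bias in the weak-link, low-stopping case (0.995).

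**The case for a change.** The strongest case for acting is that the trial is about estimation, so a reader should be able to see whether selection on completion moved the estimate. With ten pairs, one or two stoppers can move it by 4 to 8%. The random-pair model already in the plan would run on the PKS without new data, and fixing it in advance avoids a choice made after the results are known. The structural point and the arithmetic behind this stand.

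The step to a needed change does not.

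- **No sign of exposure-related stopping.** The one 15 mg discontinuation in the earlier study was put down to a common cold (Protocol 1.2 and 2.3).
- **A weak link to Day 1 is the plausible one.** Protocol 3.2 says that single-dose data do not predict steady state, and Protocol 1.2 reports a 159-fold rise in AUC0-24 by Day 28 at 10 mg and asks for caution with Day 1 AUC0-24.
- **The later endpoints gain little.** Day 28 values of a subject who stops dosing early are missing under any rule. Day 14 concerns only those who stop after that profile; its bias has not been quantified.
- **Stoppers remain visible.** They stay in the PKS geometric means and the individual listings (SAP 7), in the trial report's discussion of discontinuations (Protocol 3.3.4.1) and, if the data allow, in the regression on renal function (Protocol 7.3.2). If someone stops, the wider fit can be run from data already held.
- **Absence cannot be shown.** SAP Table 6.3:1 gives the PKS further analyses whose description is not in the public text, and the visible numbering passes over 6.4 and 7.6.

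The two enrolment triggers do differ. Read literally, Protocol 3.1 would also deny a control to a subject who finishes the Day 28 profile but misses the end-of-trial visit; Protocol 4.1.4 would not. Bringing these passages into line is a clerical matter.

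**Conclusion.** The observation is correct: an impaired early stopper leaves the Day 1 ratio, and the Day 14 ratio if sampled. No change to the plan is needed. Under the assumptions shown, the factor is 0.98 to 0.995 at CV 60% with a weak link between Day 1 exposure and stopping. It reaches 0.92 (0.88 at CV 100%) only with 20% stopping, OR 4 and Day 1 exposure fully driving the decision to stop. These lie well inside intervals of ×/÷ 1.46 and ×/÷ 1.77. No acceptance range is set (Protocol 7.2), so a shift of this size would not alter a decision rule.

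Analysing pairs only is a fair trade-off: it keeps the comparison matched, as Protocol 3.2 intends, and accepts a small, conditional selection effect on the earlier profiles. If an impaired subject does stop early, fitting the same random-pair model to all PKS subjects would be a sensible optional sensitivity result, labelled as not fully matched, with PKS-stat kept as the primary set. The conclusion rests on the assumed CVs, correlations and stopping rates, and on the absence of any sign in the documents that stopping follows exposure.

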##### **3.1.1 Administrative structure of the trial**

The trial is sponsored by Boehringer Ingelheim (BI) Pharma GmbH & Co. KG, Germany.

BI has appointed a Trial Clinical Monitor, responsible for coordinating all required activities, in order to

- manage the trial in accordance with applicable regulations and internal SOPs,
- direct the clinical trial team in the preparation, conduct, and reporting of the trial,
- ensure appropriate training and information of local clinical monitors (CML), Clinical Research Associates (CRAs), and participating trial sites.

The trial medication will be provided by the Clinical Trial Supplies Unit (CTSU), BI Pharma GmbH & Co. KG, Biberach, Germany.

The trial will be conducted at  
under the supervision of the Principal Investigator.

Safety laboratory tests will be performed by the local laboratory of the trial site

The analyses of BI 1467335 (and its metabolites and stability) concentrations in plasma will be performed at the Department of Drug Metabolism and Pharmacokinetics, BI Pharma GmbH & Co. KG, Biberach, Germany.

On-site monitoring will be performed by BI or a contract research organisation appointed by BI.

Data management and statistical evaluation will be done by BI according to BI SOPs.

Tasks and functions assigned in order to organise, manage, and evaluate the trial are defined according to BI SOPs. A list of responsible persons and relevant local information can be found in the ISF.

### **3.2 DISCUSSION OF TRIAL DESIGN, INCLUDING THE CHOICE OF CONTROL GROUP**

The study will be conducted according to a multiple-dose, open-label design with matched-groups.

BI 1467335 displays non-linear, time dependent kinetics with a 40-fold higher  $C_{max}$  and 159-fold higher  $AUC_{0-24}$  on Day 28 compared to Day 1 (see [Section 1.2](#), refers to 10 mg of BI 1467335 q.d., the dose selected for the planned study). Since steady state PK is not predicted by single dose data, multiple doses are required to assess the clinically relevant data as BI 1467335 is being developed for chronic dosing. Based on preliminary evaluation, treatment duration of 4 weeks, the currently maximum treatment duration in healthy subjects, and a dose regimen of 10 mg q.d. should provide close to steady state conditions. This should also reliably exclude any transient effects.

The resulting group sizes (see [Section 7.1](#)) are considered to be sufficient for the exploratory evaluation of pharmacokinetics. The assignment of matched healthy volunteers is a useful method to control for other factors which may influence the pharmacokinetics of BI 1467335 in a renal impaired population.

The open-label treatment is not expected to bias results, since the primary endpoints are derived from measurement of plasma concentrations of the analytes provided by a bioanalytical laboratory. It is also considered sufficiently accurate as the trial observations are objective (PK, laboratory) and over-reporting of AEs is unlikely.

### **3.3 SELECTION OF TRIAL POPULATION**

It is planned that up to 20 male and female subjects will enter the study (10 in each of two groups). Subjects with moderate renal impairment (estimated GFR based on the CKD-EPI formula 30 to 59 mL/min/1.73m^2) will be assigned to Group 1, while healthy subjects (eGFR  $\geq$  90 mL/min/1.73m^2) matched individually by gender, race, smoking status, age (within  $\pm 10\%$ ) and BMI (within  $\pm 10\%$ ) to a renal impaired subjects will be assigned to Group 2.

Proprietary confidential information © 2018 Boehringer Ingelheim International GmbH or one or more of its affiliated companies

Group 1 should include at least 25% of either gender and 5 subjects with an estimated GFR between 30 and 45 mL/min/1.73m^2.

The estimated glomerular filtration rate (eGFR) will be determined at the screening examination and on Day -2 of Visit 2 if screening was more than 10 days ago.

A log of all subjects enrolled into the trial (i.e. having given informed consent) will be maintained in the ISF at the investigational site irrespective of whether they have been treated with investigational drug or not.

### **3.3.1 Main diagnosis for study entry**

The study will be performed in moderate renally impaired subjects as well as healthy subjects.

